Most of the developmental and validation studies of the ICARS were performed in patients who were 10 years of age or older. An international study has been completed (ClinicalTrials.gov: NCT01942850) to extend its validity to patients in the age-range of 5 to 10 years. Data collected from this validation study in selected centers [Data on file, EryDel S.p.A] indicated that the distribution of scores for the ICARS for

Version 1.0, 09May2015; Version 2.1, 16Nov2015; Version 3.0 (Amend. 1), 01Feb2016; Version 3.1 (Amend. 2), 28Apr2016; Version 3.2 (Amend. 3), 25May2016; Version 4.0 (Amend. 4), 29Nov2016; Version 5.0 (Amend. 5, Site-specific), 20Sep2017; Version 6.0 (Amend. 6), 29Sep2017; Version 7.1 (Amend. 7.1), Final 13 March 2018, Version 8.0 (Amend. 8.0), Final 23 April 2018; Version 10.0 (Amend. 10), Final 16 April 2019; Version 11.0 (Amend. 11), Final 24 Jun 2020

patients with AT under 10 years of age was similar to the scores for these patients on other validated scales such as the SARA ([Schmitz-Hubsch et al, 2006b](#)) and the BARS ([Schmahmann et al, 2009](#)). Data collected from the validation study in selected centers confirmed that the severity of AT increased with age in patients under the age of 10 years, as demonstrated by a significant correlation of the total scores on the ICARS, SARA, and the BARS, but not for patients above 10 years. Overall, the distribution of scores for the ICARS for 5 to 10 year-old patients with AT was similar to the scores for other validated scales such as the SARA, BARS, CGI-S and CGI unstructured.

The variability associated with having multiple centers across different countries and languages, and multiple raters for the ICARS within each center, will be minimized by the use of central remote raters who will provide ratings of the ICARS based on video recordings of the patients' ICARS assessments performed by the site raters. These videos will be provided to the remote rater blinded to the treatment condition and in random order, without specifying the visit of the study. These remote ratings will be used in the analysis of the primary efficacy endpoint.

Although the ICARS will be rated in its entirety, the primary analyses will be limited to the 'Modified' ICARS; this version excludes Items 8-12 related to kinetic function and Items 17-19 related to oculomotor functions that are required for visual control, as these items are not directly predictive of change in functioning.

CGI-C and CGI-S

The Clinical Global Impression (CGI) consists of two 7-point, clinician-rated, Likert-type scales assessing change from baseline (CGI-C) and severity of illness (CGI-S) ([Guy, 1976](#)). In the current study, an overall assessment of the change in the patient's neurological symptoms of AT, compared to the status at baseline, will be performed at each visit and used as the key secondary efficacy measure. To ensure independence of this rating from the rating of the ICARS (the primary efficacy measure), a different rater will perform the CGI-C.

In addition, the severity of illness at baseline and at each subsequent timepoint will be assessed using the CGI-S. No version of the CGI-S exists which has been specifically adapted for use in AT patients; therefore, a 5-point structured version was developed which takes into account the severity of the following symptoms of AT: ataxia (walking), dysarthria, dysmetria, extrapyramidal symptoms (chorea, myoclonus, dystonia, and tremor), and eye movements. Ratings of none, mild, moderate, severe, and very severe are selected based on the level of symptomatology. A pilot validation study has been performed in AT patients using the CGI-S scale, and the results indicate that the CGI-S adequately discriminated patients with mild, moderate, or severe disease [Data on file, EryDel S.p.A.]. The distribution of patients to different scores on the CGI-S of AT was similar using the ICARS, BARS, and SARA in 6 to 9 year-olds. The CGI-S for patients ≥ 10 years of age was greater than in 6 to 9 year-old patients; however, the distribution of scores on the ICARS, BARS, and SARA was similar across severity categories.

Vineland Adaptive Behaviors Scale (VABS)

Functional intelligence generally is defined as one's ability to behave adaptively in daily life. Specifically, it includes the person's ability to express and comprehend language, behave appropriately in interpersonal situations, understand and use social behaviors, protect himself/herself, and care for himself/herself, in terms of personal hygiene and domestic independence. Although several scales and observation systems for measuring adaptive behavior have been developed since the 1940s, when the construct of adaptive behavior was formally introduced, one of the most widely accepted scales is the Vineland Adaptive Behavior Rating Scales (VABS; [Sparrow and Cicchetti, 1985](#); [Sparrow et al, 2005](#)).

Version 1.0, 09May2015; Version 2.1, 16Nov2015; Version 3.0 (Amend. 1), 01Feb2016; Version 3.1 (Amend. 2), 28Apr2016; Version 3.2 (Amend. 3), 25May2016; Version 4.0 (Amend. 4), 29Nov2016; Version 5.0 (Amend. 5, Site-specific), 20Sep2017; Version 6.0 (Amend. 6), 29Sep2017; Version 7.1 (Amend. 7.1), Final 13 March 2018, Version 8.0 (Amend. 8.0), Final 23 April 2018; Version 10.0 (Amend. 10), Final 16 April 2019; Version 11.0 (Amend. 11), Final 24 Jun 2020

The VABS is used primarily with children and adolescents from birth to age 18 years, but may be used for adults suspected of having a mental handicap based on obtained IQ. The scale measures adaptive behavior in four major domains, Communication, Daily Living Skills, Socialization, and Motor Skills. These domains include several subdomains, as follows:

- **Communication:** Receptive, Expressive, Written
- **Daily Living Skills:** Domestic, Personal, Community
- **Socialization:** Interpersonal Relationships, Play & Leisure, Coping Skills
- **Motor Skills:** Gross, Fine

In the current study, this scale will be used to assess the strengths and weaknesses of the AT patients in each of these specific areas of adaptive behavior which may be impacted by the disease.

QoL Scale (EQ-5D-5L)

Improvements in quality of life (QoL) are an important goal for treatment of patients with AT. Therefore, the EQ-5D-5L scale assessing QoL has been included as a secondary efficacy measure. The EQ-5D is a standardized instrument for assessing health-related QoL in a variety of health conditions ([Rabin and de Charro, 2001](#)). The EQ-5D-5L is a newer version of the scale, which includes five levels of severity for each of the five EQ-5D dimensions (Herdman et al, 2011), and has been validated in a diverse patient population in 6 countries, including 8 patient groups with chronic conditions and a student cohort (Janssen et al, 2013). For children and adolescents, the EQ-5D-5L administrators will be trained to help the younger population in the study complete the scale. Assessment of the EQ-5D-5L will be performed by the patient, or the patient's parent/caregiver, at regular intervals throughout the study.

A-T NEST

The A-T NEST represents a refinement of the A-T scale published by [Crawford et al. \(2000\)](#)¹⁷ that was developed to quantitatively describe the diverse range of abnormalities seen in patients with A-T and record their rate of progression. The development of the A-T scale was based on data collected from 52 patients with confirmed A-T attending the Johns Hopkins Hospital, who were between the ages of 1 to 19 years. Based on agreements on the ratings of video-taped examinations between 2 highly experienced raters, and the use of a weighted kappa score, principal component analysis, 9 items were selected; 2 items were dropped due to poor inter-rater agreements, and replaced by 3 other items. The final 10 items capture the essential neurologic features of the disorder.

The A-T NEST index offers advantages over other scales used to assess A-T as it was developed specifically for this disorder and thus, captures the broad range of deficits experienced by these patients. The index may be able to capture progression of the disorder faithfully. The A-T NEST scale has been used internationally over the last decade by A-T clinical experts, as part of the Ataxia Telangiectasia Children's Project (ATCP), who have made further changes and recommendations for its use internationally.

The inter-rater reliability, test-retest reliability and internal consistency have not been validated concurrently in large number of patients with A-T from multiple countries with a wide variety of raters. The ability of the A-T NEST to assess treatment-induced change has also not been determined, and there are no clinical data to suggest the magnitude of change on the A-T NEST that would constitute a clinically relevant change.

The use of the A-T NEST in this Study would allow collection of data for the validation of psychometric properties of the scale, from experienced international raters. It would also allow determination of its intra

Clinical Study Protocol IEDAT-02-2015**EDS in Ataxia Telangiectasia Patients**

Version 1.0, 09May2015; Version 2.1, 16Nov2015; Version 3.0 (Amend. 1), 01Feb2016; Version 3.1 (Amend. 2), 28Apr2016; Version 3.2 (Amend. 3), 25May2016; Version 4.0 (Amend. 4), 29Nov2016; Version 5.0 (Amend. 5, Site-specific), 20Sep2017; Version 6.0 (Amend. 6), 29Sep2017; Version 7.1 (Amend. 7.1), Final 13 March 2018, Version 8.0 (Amend. 8.0), Final 23 April 2018; Version 10.0 (Amend. 10), Final 16 April 2019; Version 11.0 (Amend. 11), Final 24 Jun 2020

and inter-rater reliability, based on the data from the CGI-S of A-T and the ICARS, and concordance of A-T NEST scores with these validated scales. Lastly, the study would help assess if the A-T NEST possesses treatment sensitivity.

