	
As a results of the COVID-19 pandemic, temporary changes to the protocol have been implemented. These changes are described in Appendix 14. Patients who are not experiencing severe side-effects, or have deteriorated significantly while on the treatment and provide informed consent will be eligible to continue treatment for an additional 6 months in a double-blind, placebo-controlled extension treatment period (or longer, in case a patient is willing to be enrolled in the open-label study IEDAT-03-2018, but the study has not yet received IRB/EC approval at the time the patient reaches Visit 15/Month 12). Patients meeting all entry criteria will be treated as follows:
 
 • Patients originally randomized to EDS-EP treatment groups (Group 1 or Group 2) will continue on the same treatment; • Patients originally randomized to the Placebo group (Group 3) will be re-randomized in equal proportions (1:1) to receive either the EDS-EP ~5-10 mg DSP/infusion or ~14-22 mg DSP/infusion, as follows: 
 ○ Following 6 months of treatment, one third of the originally randomized placebo patients will be re-randomized to treatment with EDS-EP, as described above; ○ After 9 months of treatment, one third of the originally randomized placebo patients will be re-randomized to treatment with EDS-EP, as described above; ○ At 12 months, all remaining placebo patients who continue open-label treatment will receive treatment with EDS-EP, as described above. 
The ICARS will be administered by a site rater and scoring verified by a central remote qualified rater, based on a video recording of the assessment at the site. The scores provided by the central remote raters will be used for the primary analysis of the ‘Modified’ ICARS (primary efficacy endpoint). The site ICARS rater will not be involved in the rating of the CGI-S and CGI-C, VABS, QoL or A-T NEST scale. The CGI rater will not have access to the ICARS ratings, but may refer to other scales in scoring the CGI.
 
All patients who complete 12 months of treatment in the trial, complete the study assessments, and provide informed consent will be eligible to continue treatment with EDS-EP in an open-label, extension study (IEDAT-03-2018). In case a patient is willing to be enrolled in the open-label study IEDAT-03-2018, but the study has not yet received IRB/EC approval at the time the patient reaches Visit 15/Month 12, the patient may undergo unscheduled monthly assessments/infusions (according to the assigned blinded treatment) starting from the time Visit 15/Month 12 should be performed, and continuing until the site has been initiated for the open-label study IEDAT-03-2018 and he/she has been evaluated for eligibility for the study. All patients, including those previously treated with placebo, who meet all of the selection criteria will receive monthly infusions of EDS-EP (dose range of ~14-22 mg DSP/infusion).

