The primary objective of the trial was to evaluate the effect of EDS-EP in improving neurological symptoms of AT patients over a 6-month treatment period, assessed by means of the ICARS (Trouillas et al., 1997). The ICARS is a 100-point semi-quantitative scale offering a compartmentalized quantification of the following 4 sub-scores: Posture and gait disturbances, kinetic functions, speech disorders, and oculomotor disorders. The ICARS rating was performed by a trained neurologist at baseline (before the first dose) and at 1, 3 and 6 months after the first EDS-EP administration; analysis of the change from baseline at each visit was performed on the ITT population using Repeated Measures Analysis of Variance (RMANOVA). Secondary objectives of the trial were to evaluate the safety profile of EDS-EP through the assessment of TEAEs, including steroid-dependent adverse reactions, SAEs, standard laboratory parameters, physical examination, vital signs, ECGs and concomitant medications and procedures. Additionally, the effects of EDS-EP were assessed on the patients' global health status (IGA), ocular motility, and adaptive behaviour (VABS). The effect of EDS-EP on special laboratory parameters, i.e. total cholesterol, HDL, LDL, blood glycosylated hemoglobin (HbA1c), CD4+ lymphocytes counts, α -fetoprotein, urinary cortisol and plasma cortisol, was also measured.

Methods

Patients providing informed consent (along with consent of their parents or legal guardian, as required) entered a 30-day screening period, during which any prior corticosteroid treatment was withdrawn. Medical history and demographic information was collected, and physical and neurological examinations, vital signs, ECG and standard laboratory tests were performed. Patients meeting all selection criteria were enrolled in the treatment period and had the physical examination, vital signs and laboratory tests repeated and all efficacy evaluations performed at baseline (Day 0) prior to receiving the first of 6 monthly infusions of EDS-EP. The amount of DSP added to the 50 mL of the subject's blood in the encapsulation procedure was kept constant for all patients, i.e. 500 mg/20 mL DSP solution, and was expected to deliver approximately 10-15 mg of DSP by using the previous EDS version 3.1.2 over the one-month period between doses.

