A physical examination, vital signs and routine laboratory tests were performed at each monthly visit. The primary efficacy measure (ICARS) was assessed at one month, and at the 3-month visit, all efficacy assessments were done, along with the special laboratory tests (before drug infusion). A final evaluation was performed at 6 months after the initial infusion (one month after the last dose), during which all efficacy and safety assessments were performed. The occurrence of any AEs and the use of concomitant medication were recorded from the time of signing of the consent form until the end of the study. Blood samples for the PK analysis were collected from selected patients prior to dosing (0 hr), and at 4 hours and 15 and 30 days post-dose for the first and fourth infusions.

Version 1.0, 09May2015; Version 2.1, 16Nov2015; Version 3.0 (Amend. 1), 01Feb2016; Version 3.1 (Amend. 2), 28Apr2016; Version 3.2 (Amend. 3), 25May2016; Version 4.0 (Amend. 4), 29Nov2016; Version 5.0 (Amend. 5, Site-specific), 20Sep2017; Version 6.0 (Amend. 6), 29Sep2017; Version 7.1 (Amend. 7.1), Final 13 March 2018, Version 8.0 (Amend. 8.0), Final 23 April 2018; Version 10.0 (Amend. 10), Final 16 April 2019; Version 11.0 (Amend. 11), Final 24 Jun 2020

Disposition

A total of 26 patients with AT were screened and 22 were enrolled in the study, representing the ITT population. Four subjects discontinued prematurely; one withdrew consent, another patient was dropped due to a protocol violation (CD4+ lymphocytes below cut-off at baseline), and 2 patients experienced laboratory abnormalities (decrease in CD4+ lymphocytes count) that led to their withdrawal.

Demographics and Disease Characteristics

The mean (SD) age of the AT patients was 11.2 (3.5) years, with 11 (50%) patients being males. All patients were Caucasian with a mean weight of 29.1 (9.5) kg and BMI of 15.6 (2.6). The average age of diagnosis of AT was 60.0 (35.2) months, with a mean age of symptom onset of 25.9 (17.5) months. The mean baseline scores for the ICARS and VABS were 50.6 (12.8) and 5.5 (2.0), respectively. Mean baseline scores on the sub-scales of the ICARS were as follows: posture/gait disturbance – 20.9 (7.1); kinetic function – 23.1 (6.2); speech disorders – 3.5 (1.4); and oculomotor disorders – 3.2 (1.0). Two patients were on inhalational steroids at screening, and these medications were discontinued.

Efficacy Results

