Sixteen patients (72.7%) received all 6 infusions of EDS-EP, as planned. Results for the primary efficacy measure (change from total baseline ICARS score) for the ITT population (n=22) indicated an overall statistically significant ($p=0.02$, RMANOVA) improvement with EDS-EP treatment. Significant improvement was observed after 3 and 6 months of treatment with EDS-EP for the kinetic sub-score of the ICARS, the clinician rated the Investigator Global Assessment (IGA), adaptive behavior (as assessed by the VABS) and ocular motility.

Secondary analyses. The mean DSP dose/infusion was 7.5 ± 1.8 mg. There was however, substantial variability in the patient-specific DSP encapsulation in erythrocytes, with mean doses of DSP measured in the EDS-EP for each subject ranging from 0.7 ± 0.1 to 18.6 ± 1.9 mg (patients received 6 doses). Additional analyses were performed to determine if there was a relationship between DSP dose and efficacy response. In these analyses, patients were categorized as “loaders” if their mean DSP dose was 5 mg or higher. Loaders (64%) as compared to non-loaders (27%) showed a clinically significant improvement on the ICARS (defined as $> 10\%$ improvement versus baseline) at 6 months. Loaders had a mean percent decrease (improvement relative to baseline) of -14.4% for the ICARS total score, compared to -4.7% for non-loaders.

Safety Results

The safety population included all 22 patients. Overall, 15 (68.2%) of patients experienced at total of 29 TEAEs, most of which were rated as mild (~60% of subjects) and not related to the study medication ($> 90\%$ of patients), with the exception of 1 patient with a mild hypercholesterolemia. Two SAEs were reported during the study, including one case of severe pneumonia and a second patient with bronchopneumonia, and bronchiectasis and bleeding; both patients required hospitalisation. Both cases were considered unrelated to study medication and resolved with treatment.

Two patients had a $> 20\%$ decrease in CD4+ lymphocytes count during the study period which resulted in premature discontinuation, and were considered related to study medication.

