Children with AT may have a lower body weight compared to age-matched controls; therefore, the minimum weight requirement was lowered to 15 kg. CD4+ lymphocyte counts have been included to assess the immune status of these patients as the ATM gene compromises their ability to combat infections. CD4+ lymphocyte cut-off limits have been proposed stratified by age as recommended by AT experts. Patients whose counts are consistently below 150/mm³ (for patients > 6 years), or below 200/mm³ (for patients > 6 years and in presence of oral infections, like oral candidiasis, documented at the screening or recurrent as per medical history/adverse events documentation) or below 400/mm³ (for patients 6 years of age) during treatment will have their treatment interrupted.

The exclusion criteria for the study are designed to exclude patients who would be at increased risk for an adverse outcome related to treatment with EDS-EP or their participation in the trial due to their medical history/current status or use of concomitant medication. Dexamethasone has teratogenic potential in rodents; therefore, females of childbearing potential will be included only in case they are practicing adequate contraception as described at section 9.2.2. Pregnant women will be excluded. Dexamethasone is excreted in breast milk; therefore, patients who are breast-feeding are also excluded. Patients with AT are at increased risk of neoplastic and immunological diseases due to the decreased ability of the ATM gene to repair DNA; therefore, patients with these conditions are excluded. Patients who are currently on steroids or have taken them within the last month, are excluded, as their effects may confound the assessment of the efficacy and safety of EDS-EP.

Rationale for the Study Design

Double-blind Design

The double-blind design is being used to minimize the systematic bias in ratings of efficacy that may result from the rater, patient or caregiver knowing the treatment that the patient is receiving. The double-blind design also minimizes bias in assessing the potential relationship of safety findings to the study treatments.

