11.5 Visit Schedule and Assessments – Extension Treatment Period

11.5.1 Month 6 (Visit 9)

Final evaluations for the 6-month Initial Treatment Period will serve as baseline evaluations for patients continuing in the 6-month Extension Treatment Period.

- a) Obtain written informed consent for the extension period
- b) Randomized switch of one-third of placebo patients to EDS-EP treatment
- c) 1 mL blood collected, after blood diversion, for aerobic culture
- d) Autologous blood collection for EDS processing
- e) Upon completion of the EDS process, fill the satellite sample bag with approximately 6 mL of EDS-EP by gravity (approximately 2 mL if no other samples but the ones for sterility culture test will be collected).
- f) **CCI** [REDACTED]

- h) Hemolysis panel [free plasma hemoglobin, haptoglobin, bilirubin (total and conjugated), LDH]
- i) Urine pregnancy test will be performed before infusion (for women of childbearing potential)
- j) Review of AEs – reported by the patient or observed by the Investigator
- k) Review of concomitant medication
- l) **Infusion of EDS-EP autologous RBCs.**

Post-infusion

- m) Physical examination
- n) Vital signs
- o) Hemolysis panel [free plasma hemoglobin only, 1 hr post-infusion]

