11.6 Laboratory Sample Collection

Revised study procedures to ensure sterility of the EDS-EP

New aseptic procedures have been implemented to ensure sterility during blood collection for the EDS process, the various steps of the EDS process, sample collection for routine laboratory tests, sample collection from the EDS-EP for sterility testing, and administration of the EDS-EP to the patient. Details of these procedures are described in a separate document entitled “Revised Study Procedures on Sterility Testing for Study IEDAT-02-2015 (ATTeST)”, which will be provided to each site (see [Appendix 13](#)). These new procedures include the following measures that must be performed to ensure sterility:

- Blood sampling under sterile conditions.
- Careful hand washing and use of fresh (non-sterile) gloves for each patient, disinfected frequently using a bactericidal rub.
- Frequent and repeated use of a bactericidal solution, including the mandatory use of 2% chlorhexidine in 70% isopropyl alcohol for disinfection of the skin at the venipuncture site, or

Version 1.0, 09May2015; Version 2.1, 16Nov2015; Version 3.0 (Amend. 1), 01Feb2016; Version 3.1 (Amend. 2), 28Apr2016; Version 3.2 (Amend. 3), 25May2016; Version 4.0 (Amend. 4), 29Nov2016; Version 5.0 (Amend. 5, Site-specific), 20Sep2017; Version 6.0 (Amend. 6), 29Sep2017; Version 7.1 (Amend. 7.1), Final 13 March 2018, Version 8.0 (Amend. 8.0), Final 23 April 2018; Version 10.0 (Amend. 10), Final 16 April 2019; Version 11.0 (Amend. 11), Final 24 Jun 2020

during handling of the venous catheter (if used), and for disinfecting ports, connectors and working surfaces/environments.

- CCI [REDACTED]
- [REDACTED]
- [REDACTED]
- [REDACTED]
- [REDACTED]
- [REDACTED]
- [REDACTED]
- [REDACTED]
- [REDACTED]

Blood sampling

Venous blood samples will be drawn for routine safety evaluations (hematology and clinical chemistry). The maximum volume of blood drawn for laboratory analyses on any one day will be approximately 68 ml:

- 1.0 mL for hematology tests [Screening, Day 0 (optional) and Months 3, 6, 9 and 12]
- 5.0 mL for clinical chemistry [Screening, Day 0 (optional) and Months 6 and 12]
- 3.5 mL for clinical chemistry [Day 0 (optional) and Months 3 and 9]
- 1.0 mL for CD4+ lymphocytes tests (Screening, Day 0, Month 6 (pre-dose), and Month 12); samples for alpha fetoprotein, C-reactive protein, and Hb1Ac to be taken at same timepoints from blood collected for clinical chemistry or hematology.

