13.5 Special Laboratory Evaluations

Measurement of selected “special” laboratory parameters has been included in the study to evaluate potential effects of dexamethasone (EDS-EP) treatment (for details on aseptic procedure for blood withdrawal and on blood diversion see “Revised Study Procedures on Sterility Testing for Study IEDAT-02-2015 (ATTeST)”; [Appendix 13](#)). The following special laboratory parameters will be assessed in the study:

- Blood glycosylated hemoglobin (HbA1c, %), CD4+ lymphocytes, α -fetoprotein (not repeated at baseline), C-reactive protein (CRP), and RBC antibodies (IgG, IgM, Qualitative Direct Coombs test) (not repeated at baseline)– to be performed at Screening and Baseline (Day 0) and on Months 6 and 12 (or at early discontinuation).
- Screening for adrenal insufficiency will be performed in all patients, regardless of weight, via early morning (before 8:00 AM) plasma cortisol testing at the following times: (1) during the screening period (prior to randomization), (2) when patients are symptomatic, and (3) when patients are at most risk for adrenal insufficiency and adrenal crisis, such as following discontinuation or interruptions of dexamethasone dosing (i.e., loading failures and following discontinuation of the study drug). If the 8:00 AM cortisol level is below 3-5 $\mu\text{g/dL}$ (depending on assay) regardless of symptoms, or the patient exhibits signs or symptoms of adrenal insufficiency ([Appendix 12](#)) and has a cortisol $<10 \mu\text{g/dL}$, the patient will receive a high dose ACTH stimulation test, regardless of weight, within 24 hours. If the ACTH stimulation test is normal, the patient can be enrolled, or can continue dosing with EDS-EP, after the effects of the ACTH have dissipated (e.g., 30 days after ACTH administered). If the patient fails the ACTH stimulation test they will be excluded or discontinued from the study and referred to a pediatric endocrinologist, with a recommendation to prescribe stress dose steroids.

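### The rule to interrupt treatment for consistently low CD4 counts cannot work from scheduled tests, because only one count falls between the first and last planned infusions

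*Protocol*

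**What the plan says.** Section 7.3 of the protocol (rationale for the patient population) sets CD4 limits that apply on treatment: 150/mm³ for patients over 6 years, 200/mm³ for those over 6 with oral infections, and 400/mm³ at age 6. Patients consistently below the limit that applies to them are to stop dosing; the sentence ends "for patients 6 years of age) during treatment will have their treatment interrupted". It does not say how many low counts, or over what period, make a result consistent.

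The sampling times are given elsewhere and agree with one another. Section 13.5 says the special laboratory tests, CD4 among them, are "to be performed at Screening and Baseline (Day 0) and on Months 6 and 12 (or at early discontinuation". Section 11.6 lists "1.0 mL for CD4+ lymphocytes tests (Screening, Day 0, Month 6 (pre-dose), and Month 12". The synopsis and Tables 2A and 2B match. Months 3 and 9 have hematology, which includes total lymphocytes, but no CD4 count.

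For the extension, the synopsis and section 11.2 say "Patients meeting all entry criteria will be treated as follows". Section 11.5.1 says only "Final evaluations for the 6-month Initial Treatment Period will serve as baseline evaluations for patients continuing in the 6-month Extension Treatment Period" and lists no eligibility review.

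Section 7.1.3.1 describes the phase II study in the same disease. Among its aims: "The effect of EDS-EP on special laboratory parameters, i.e. total cholesterol, HDL, LDL, blood glycosylated hemoglobin (HbA1c), CD4+ lymphocytes counts". On timing: "at the 3-month visit, all efficacy assessments were done, along with the special laboratory tests (before drug infusion". Two patients there had a fall of more than 20%, a "decrease in CD4+ lymphocytes count during the study period which resulted in premature discontinuation, and were considered related to study medication".

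**The concern.** The rule is mandatory in wording, but the schedule does not supply the data to trigger it. Consistency needs at least two counts. Screening and Day 0 come before any treatment, and low values there exclude the patient under criterion 4. Month 12 comes after planned dosing has ended. That leaves Month 6 alone.

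Section 13.5 gives draw times for CD4 but no threshold, repeat or action. For cortisol, the same section gives all three.

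The treatment is a steroid given to immunodeficient patients, including children from age 6, and the sponsor's own phase II study had drug-related stops for CD4 falls. A fall that starts after infusion 1 would first be looked for after six infusions, and acting on it would then depend on a test that nobody is required to order. What is at stake is patient safety, not the efficacy conclusion.

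**Working it through.** **Inputs.** Infusion 1 is on Day 1, infusions 2–6 at Months 1–5, infusion 7 at Month 6 and infusions 8–12 at Months 7–11 (sections 9.3 and 11.2, Tables 2A and 2B). Spacing is at least 21 days and at most 28 + 10 = 38 days (section 11.2; SAP section 1.3). CD4 is drawn at Screening, Day 0, Month 6 (pre-dose) and Month 12.

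**Time to the first on-treatment count.**
- Day 1 to Month 6 is six intervals: 6 × 21 = 126 days to 6 × 38 = 228 days. SAP section 1.3 also gives 228 as the maximum.
- With a Month 3 count it would be three intervals: 3 × 21 = 63 to 3 × 38 = 114 days.
- Infusions 7 to 12 span five more intervals, 105 to 190 days, with no scheduled count after the pre-dose Month 6 draw.

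**Scheduled counts after the first and before the last planned active infusion.**

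| Patients | Now | With Months 3 and 9 added |
|---|---|---|
| Active from the start | 1 (Month 6) | 3 (Months 3, 6, 9) |
| Switched at Month 6 | 0 (switch-day count exists) | 1 (Month 9) |
| Switched at Month 9 | 0 (latest count 63–114 days before the switch) | 0 (switch-day count gained) |

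SAP Table 5 plans 10 + 10 switches at Visit 9 and 10 + 10 at Visit 12, so 40 of 60 placebo patients. With 175 randomized, and assuming equal arms and no dropout, 175/3 × 2/3 = 38.9, about 39.

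**Phase II experience.** 2/22 = 9.1%, exact (Clopper–Pearson) 95% CI 1.1% to 29.2%. The criterion there was a relative fall of more than 20%, so this rate cannot be turned into a number of patients below the absolute limits of section 7.3.

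**Blood volume.** Section 13 says draw frequency was modified to meet pediatric guidelines, so an added draw has to be checked against the section 11.6 volumes. Figures are mL of laboratory blood, without optional Day 0 repeats, the ~50 mL processing draw or the 1 mL culture.
- Month 3: hematology 1.0 + chemistry 3.5 + free hemoglobin 2.0 + haptoglobin 3.5 + PK 6.0 = 16.0, rising to 17.0.
- Month 9: 1.0 + 3.5 + 2.0 + 3.5 = 10.0, rising to 11.0.
- Month 6, unchanged: hematology 1.0 + chemistry 5.0 + CD4 1.0 + RBC antibodies 1.0 + free hemoglobin 2.0 + haptoglobin 3.5 + mini-ATM 2.5 + PK 3.0 = 19.0.
- Heaviest 56-day window at 21-day spacing: Day 0/1 (11.5) + Day 2 (8.5) + Day 15 (8.5) + Month 1 (4.0) + Month 2 (9.5) = 42.0, plus three processing draws.
- Heaviest window containing Month 3: 8.5 + 4.0 + 9.5 + 16.0 = 38.0, rising to 39.0 (40.0 with one repeat), plus three processing draws.
- Heaviest window containing Month 9: 12.0, rising to 13.0.

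Counts at Months 3, 6, 9 and 12 are at least 63 days apart, so no 56-day window gains more than one scheduled draw. The heaviest 8-week total does not rise.

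**The case against.** The strongest reply is that section 7.3 does not confine the rule to scheduled tests. Section 13.4 requires the investigator to review laboratory reports within 24 hours of receipt and to repeat a clinically significant abnormal result if needed. A low Month 6 count followed by a repeat would satisfy the rule with infusions still to come. On this view the gap is one of wording. It stands that the rule can be met off schedule. But the repeat is discretionary and untimed, and it needs a first low count to prompt it, which cannot come from a scheduled test before Month 6. No text found makes infusion 7 wait for a result from the central laboratory.

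Other safeguards exist: total lymphocytes at Months 3, 6, 9 and 12, a CD4 count at early discontinuation, withdrawal for adverse events under section 15.2, low CD4 as a steroid-related event of interest in SAP section 5.4.1, and DSMB meetings at most three months apart. None of these supplies a further CD4 count during dosing to set against the section 7.3 limits.

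Section 7.1.3.1 also reports no clinically meaningful change in the special laboratory parameters other than urinary cortisol. That is an overall finding and does not undo two individual stops judged drug-related. Unscheduled draws in phase II cannot be excluded, so it is an inference that the 3-month test found them.

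Two further points stand in part. Added draws alone leave Month 6 switchers with one count and Month 9 switchers with none before their last active infusion, so the mandatory repeat carries much of the remedy. And protocol version 11.0 is dated 24 June 2020, after enrollment closed on 30 March. A patient enrolled that day would reach Month 3 between 1 June and 22 July without delays, so under this version a Month 3 draw would reach few patients. The Month 9 draw and the repeat rule keep their value.

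**Conclusion.** The concern holds. Scheduled testing gives one on-treatment CD4 count before planned dosing ends, 126 to 228 days after the first infusion, and no scheduled pair of counts can show a consistently low value in time. About 39 switched placebo patients (equal arms and no dropout assumed) have no scheduled count between their first and last planned active infusions.

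This rests on the body of the protocol and the SAP. Appendices 4 (clinically notable values) and 14 (COVID-19 changes) were not available and could contain a trigger or extra tests. No number of patients who would cross the limits is projected. Sample size, power, the efficacy analysis and type I error are unaffected. It is an inexpensive safety correction worth making.

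**What to change.** 1. Add a 1.0 mL CD4 count to the existing Month 3 and Month 9 hematology draws, for all patients so that the blind is kept.
2. In section 13.5, state the limits, require a count below them to be repeated and resolved before the next infusion, and state the action.
3. State whether the extension entry condition in the synopsis and section 11.2 re-applies exclusion criterion 4, and whether infusion 7 waits for the Month 6 result.

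Items 1 and 2 together make the rule work. Item 3, or a definition of consistently low on its own, would only clarify it. A further count for Month 9 switchers, for example with the Month 10 or 11 creatinine draw, is an optional clinical decision. The sponsor and its clinical experts should set the limits.

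The cost is two 1.0 mL assays per patient, a repeat for those with a low count, some protocol wording and occasional short dosing delays. The pediatric blood-volume limit itself is not stated in the text, so the sponsor should confirm that the added draws stay within it.
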